7.3. Lost to Follow up

A participant will be considered lost to follow-up if he/she fails to complete the final 12 month visit and is unable to be contacted by the study site.

The following actions must be taken if a participant fails to return to the clinic for a required study visit:

- The site must attempt to contact the participant and reschedule the missed visit as soon as possible and ascertain whether the participant wishes to and/or should continue in the study.
- Before a participant is deemed lost to follow-up, the investigator or designee must make every effort to regain contact with the participant (where possible, [3] telephone calls, and if necessary, a certified letter to the participant's last known mailing address or local equivalent methods). These contact attempts should be documented in the participant's medical record.
- Should the participant continue to be unreachable, he/she will be considered to have withdrawn from the study.
- Site personnel will attempt to collect the vital status of the participant within legal and ethical boundaries for all participants randomized, including those who did not get study intervention. Public sources may be searched for vital status information. If vital status is determined as deceased, this will be documented and the participant will not be considered lost to follow-up.

8. Study Assessments and Procedures

Patient eligibility will be evaluated. Eligible patients who express interest in participating and express informed consent will undergo enrollment and randomization. Patients can be enrolled in the inpatient setting during an acute care encounter or in the outpatient setting so long as their new-onset atrial fibrillation was diagnosed in the prior 120 days. Atrial fibrillation can be documented by any electrocardiographic technology that provides an electrocardiographic tracing. Appropriate methods of diagnosis include a standard 12 lead electrocardiogram, mobile ECGs, ambulatory monitoring (e.g. Holter), telemetry, or electrograms from cardiac implanted electronic devices (i.e. pacemaker). At the baseline encounter (enrollment and randomization) data on the inclusion and exclusion criteria will be recorded in REDCap and the randomization module in REDCap will assign a treatment arm if participant meets all inclusion and exclusion criteria. The GWTG-AFIB registry data and additional data on the patient's medical and cardiovascular history will be recorded in the Get With The Guidelines CHANGE AFIB case report form. There are no special laboratory testing procedures or interventional procedures required by the protocol other than the randomized treatment. All data, including electrocardiographic, echocardiographic, laboratory, and other baseline data will be obtained as part of the participant's usual care. The two quality-of-life measures will be recorded at baseline and the 12 month follow-up visit as well as previously detailed.

There are two pre-specified follow-up encounters. The first will occur at 6 months with an eligibility window between 3 and 9 months. This encounter can be either in-person or a virtual assessment. At the 6-month visit, the 6-month follow-up form will be completed in the Get With The Guideline CHANGE AFIB case report form. The second pre-specified encounter will be the final follow-up encounter at 12 months (window of ± 30 days). Similar to the 6 month encounter, the final visit can be either in-person or a virtual assessment. At this final follow-up visit, the final visit module will be completed in the Get With The Guideline CHANGE AFIB case report form. Participants will also complete the final quality-of-life assessments at this same encounter. Patients who withdraw early or experience mortality will also have the final follow-up form completed.

8.1. Outcomes Assessments

Planned timepoints for all assessments are provided in the assessment table. Get With The Guidelines (GWTG) has several quality control assessments. Bi-annual data quality reports are provided by Duke Clinical Research Institute, which highlight the health of the GWTG data set, levels of element completion, and any areas of inconsistency. GWTG has an annual audit process, where a random sample of hospitals are selected for chart re-abstraction to independently assess data quality. GWTG sites are trained on the detailed data definitions provided to sites. Sites will be familiar and comfortable with the level of detail provided in the data definitions for various CHANGE AFIB endpoints. A nationwide audit was conducted among 147 hospitals and results were published in the *American Heart Journal* validating the health and reliability of the GWTG data set.⁶¹

8.1.1. Pregnancy

Women of reproductive age should use measures to prevent pregnancy during the study. Nevertheless, in case of pregnancy, the sponsor and coordinating center should be notified immediately. Follow-up of the pregnancy will be mandatory until the outcome has been determined. Pregnancy will be recorded as an adverse event in all cases and dronedarone should be immediately discontinued. Pregnancy will be considered a severe adverse event only if it fulfills the severe adverse event criteria.

8.2. Adverse Events (AEs) Serious Adverse Events (SAEs), and Other Safety Reporting

All participating centers will receive adequate training regarding pharmacovigilance (PV) specifications and reporting of adverse events among patients taking dronedarone as part of their onboarding process. Due to the pragmatic nature of the study, all Adverse Events should be reported by the individual facilities, as instructed by current regulations. Participating centers will be responsible to inform Sanofi of any Adverse Events or product technical complaints (i.e., changes in tablet odor, color, taste etc.) to Sanofi PV via email at [contact]. In the event of email failure, adverse events can also be sent by e-Fax Number ([contact]) or fax machine at ([name]) immediately, but in any event within three business days after becoming aware of the adverse event. Any additional documentation of these cases will be conducted by Sanofi U.S. PV.

Prior clinical trials and observational data have demonstrated that individuals taking dronedarone have higher rates of diarrhea (9% vs 6% in ATHENA), bradycardia (3% versus 1% in ATHENA), QT-interval prolongation^{††} (28% vs 19%) and cutaneous rash (5% versus 3%) than patients taking placebo. The case report form will query and document the occurrence of these and other adverse/safety events of interest as shown in **Table 3**.

Table 3. Pre-specified Safety Events of Interest
Symptomatic bradycardia
2 nd or 3 rd degree atrioventricular block
Pacemaker implantation
QT prolongation
Cutaneous rash

^{††} QT prolongation was defined as QTc Bazett >450 msec in males or >470 msec in females.

Hepatic injury. Hepatic injury will be defined as AST or ALT greater than 3x the upper limit of normal or clinical findings of hepatic insufficiency (jaundice, ascites, etc).
New-onset heart failure (Note that this event is also an efficacy endpoint)
Heart failure hospitalization (Note that this event is also an efficacy endpoint)
Ventricular arrhythmia (including sustained ventricular tachycardia or nonsustained polymorphic VT/torsades)
Major bleeding. Note Major bleeding will be defined according to International Society on Thrombosis and Haemostasis (ISTH) criteria: 1) Fatal bleeding, and/or 2) Symptomatic bleeding in a critical area or organ (intracranial, intraspinal, intraocular, retroperitoneal, intra-articular or pericardial, or intramuscular with compartment syndrome), and/or 3) Bleeding causing a fall in hemoglobin level of 20 g L⁻¹ (1.24 mmol L⁻¹) or more, or leading to transfusion of two or more units of whole blood or red cells.⁶²

Initiation of dronedarone is contraindicated in patients with severe heart failure (NYHA class IV) or NYHA Class II - III heart failure with a recent decompensation requiring hospitalization or referral to a specialized heart failure clinic in the prior 4 weeks. Similar patients in the ANDROMEDA trial receiving dronedarone were observed to have a greater than 2-fold increase in mortality compared to placebo.³⁰ Accordingly, patients with NYHA class III and IV heart failure or any individual with a heart failure hospitalization in the last 4 weeks will be excluded from the trial. Additionally, any patients with an ejection fraction less than or equal to 40% will be excluded from the trial. The trial will document hospitalization for new or worsening heart failure during the follow-up period. It is important to note that dronedarone competes with creatinine for the renal tubular cation transport pathway, inhibiting tubular secretion of creatinine by approximately 18% and subsequently increasing serum creatinine without affecting renal function. This is of importance when considering down-titration/discontinuation of ACE/ARBs.

9. Statistical Considerations

The statistical analysis plan will be finalized before the first data and safety monitoring board (DSMB) meeting with blinded review of data, and it will include a more technical and detailed description of the statistical analyses described in this section. This section is a summary of the planned statistical analyses of the most important endpoints including primary and key secondary efficacy endpoints, patient reported outcomes, and key safety outcomes.

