5.2. Exclusion Criteria

Participants are excluded from the study if any of the following criteria apply:

1. Patients with prior or planned treatment with rhythm control, either catheter ablation or chronic (>7 days) antiarrhythmic drug therapy.**
2. Planned cardiothoracic surgery
3. New York Heart Association class III or IV heart failure or a hospitalization for heart failure in the last 4 weeks
4. Patients with reduced ejection fraction (LVEF \leq 40%)
5. Permanent atrial fibrillation
6. Ineligible for oral anticoagulation, unless CHA₂DS₂-VASc is less than 3 in women or 2 in men.
7. Bradycardia with a resting heart rate < 50 bpm
8. PR interval >280 msec or 2nd degree or 3rd degree atrioventricular block without a permanent pacemaker/cardiac implanted electronic device.
9. Corrected QT interval \geq 500 msec.
10. Pregnancy or breast feeding
11. Severe hepatic impairment in the opinion of the investigator

§ Electrocardiographic documentation includes a standard 12 lead electrocardiogram, mobile ECGs, ambulatory monitoring (e.g., Holter), telemetry, or electrograms from cardiac implanted electronic devices (i.e., pacemaker).

** Acute use of an antiarrhythmic drug in the hospital is not exclusionary. For the purpose of this trial, prior antiarrhythmic drug therapy is defined as chronic antiarrhythmic drug therapy (>7 days).

6. Study Intervention, Usual Care, and Concomitant Therapy

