The study intervention will be treatment with oral dronedarone 400 mg twice daily in addition to usual care. The comparator arm will be usual care alone. Usual care will be defined as best-practice, guideline-directed therapy of AF, including but not limited to (a) stroke prevention therapy, (b) rate-control, and (c) treatment of risk factors. More specifically, oral anticoagulation in those men with a CHA₂DS₋₂VASc score of 2 or greater or women with a CHA₂DS₋₂VASc score of 3 or greater, rate control, and treatment of concomitant cardiovascular conditions (e.g. coronary artery disease or heart failure) will be required in all trial participants. As defined in the protocol, those randomized to the dronedarone arm will be prescribed 400 mg oral dronedarone twice daily. Similar to the approach in the EAST trial, those randomized to usual care alone will initially be treated without rhythm-control therapy¹⁴, however rhythm-control therapy (except dronedarone) may be initiated during follow-up in the usual care arm to ameliorate AF-related symptoms despite adequate rate-control therapy per current guideline recommendations. In the dronedarone arm concomitant digoxin use is contraindicated due to P-gp interaction based upon data from the PALLAS trial.²⁹

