9.3.7. Other Analyses

On treatment analysis of efficacy endpoints

As sensitivity analyses, the primary and key secondary objectives will be tested using the OT population during the on-treatment period.

Pre-Specified Subgroups of Interest

Subgroup analyses for the primary outcome will be performed to assess whether the therapeutic effect is consistent across all patients, or whether it varies according to specific patient

characteristics. These analyses will focus on whether the relative therapeutic effect differs according to the following baseline variables:

- Age (<70 years vs. ≥70 years)
- Sex (male vs. female)
- Race (white vs. racial minorities)
- AF type (paroxysmal vs. persistent, or long-standing persistent)
- Left atrial dimension (<50 mm versus ≥50 mm)
- AF duration (<30 days versus ≥30 days)
- Structural heart disease (present vs. absent)
- Hypertension (present vs. absent)
- Chronic kidney disease (estimated eGFR ≤60 vs. >60 ml/min)
- CHA₂DS₂-VASc score (0-1 vs. ≥2 excluding sex)
- Sleep Apnea (present vs. absent)
- BMI (<30 vs. ≥30)
- Heart failure vs no heart failure
- Left ventricular ejection fraction (LVEF) (41-55 vs. >55)
- Recent hospitalization for AF vs None

Cox proportional hazards regression modeling will be used to assess whether treatment effect is heterogeneous across pre-specified subgroups. For each subgroup analysis, the Cox proportional hazards model will be fit for time to first event including the subgroup as a stratification factor, and the treatment group and interaction between treatment and subgroup as covariates. The treatment effect within each subgroup level will be presented as a hazard ratio (dronedaron on top of usual care vs. usual care) and a 95% CI. Heterogeneity will be assessed by presenting the interaction P-value, using a two-sided test.

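### Exclusion 3 leaves out the clinic-referral part of the heart failure contraindication it is meant to implement, so one type of patient is both contraindicated and eligible

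*Protocol*

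**What the plan says.** Protocol Section 8.2 states when starting dronedarone is contraindicated: in NYHA class IV, or in "NYHA Class II - III heart failure with a recent decompensation requiring hospitalization or referral to a specialized heart failure clinic" within the prior 4 weeks. It supports this by noting that similar patients given dronedarone in the ANDROMEDA trial had more than twice the mortality seen on placebo.

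The next step in Section 8.2 turns this into an exclusion: "Accordingly, patients with NYHA class III and IV heart failure or any individual with a heart failure hospitalization in the last 4 weeks" are kept out of the trial, as is anyone with an ejection fraction of 40% or lower. Item 3 in Section 5.2 and in the Synopsis has the same content: "New York Heart Association class III or IV heart failure or a hospitalization for heart failure in the last 4 weeks". Item 4 is the ejection fraction limit. None of the 11 exclusions mentions clinic referral, and none is a general criterion for contraindications to dronedarone.

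Two further passages show how the list is used. Section 8 says that "the randomization module in REDCap will assign a treatment arm if participant meets all inclusion and exclusion criteria". Section 6 says that "those randomized to the dronedarone arm will be prescribed 400 mg oral dronedarone twice daily".

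**The concern.** The contraindication has two triggers for a recent decompensation, hospitalization and specialist referral. The exclusion presented as following from it has only the first. A site that applies the eligibility list exactly could randomize a recently decompensated patient to a drug that the same protocol says must not be started in that patient.

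The referral trigger appears only in the adverse-event section, away from the place where sites check eligibility. Heart failure exacerbation is among the known risks listed in Section 2.2.1, so this is a patient-safety matter.

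**Working it through.** No figure in the protocol needs reproducing here. The check crosses the two rules and looks for patients who meet the contraindication but no exclusion.

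**Inputs**
- Contraindicated (Section 8.2): NYHA IV; or NYHA II–III with a decompensation in the prior 4 weeks leading to hospitalization or to referral.
- Excluded (Section 5.2, items 3 and 4): NYHA III–IV; or heart failure hospitalization in the last 4 weeks; or LVEF 40% or lower.

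**Grid.** NYHA class (I, II, III, IV) × decompensation in 4 weeks (none, hospitalized, referred only) × LVEF (40% or lower, above 40%) = 4 × 3 × 2 = 24 profiles, 6 per class.

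| NYHA | Contraindicated | Excluded | Both | Contraindicated but eligible | Excluded but not contraindicated |
|---|---|---|---|---|---|
| I | 0 | 4 | 0 | 0 | 4 |
| II | 4 | 4 | 3 | 1 | 1 |
| III | 4 | 6 | 4 | 0 | 2 |
| IV | 6 | 6 | 6 | 0 | 0 |
| Total | 14 | 20 | 13 | 1 | 7 |

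- Contraindicated: NYHA IV gives 3 × 2 = 6; NYHA II and III with hospitalization or referral give 2 × 2 × 2 = 8; total 14.
- Excluded: NYHA III–IV give 2 × 3 × 2 = 12; NYHA I–II hospitalized give 2 × 2 = 4; NYHA I–II not hospitalized with low LVEF give 2 × 2 = 4; total 20.
- The uncovered cell (14 − 13 = 1) is NYHA II, referred only, LVEF above 40%.

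A finer grid adds patients without heart failure and treats hospitalization and referral as separate yes/no items: 5 × 2 × 2 × 2 = 40 profiles. It isolates the same single profile. The other nine exclusions in Section 5.2 do not address it.

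**Can such a patient reach randomization?** NYHA I–II heart failure is not excluded. Section 8 allows enrollment in the outpatient setting, where a patient who was referred but not admitted could be seen. Section 9.3.7 plans a subgroup analysis of "Heart failure vs no heart failure" and another of LVEF 41–55 versus above 55.

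**With referral added to exclusion 3**, two more profiles are excluded: NYHA I and NYHA II, each referred only with LVEF above 40%. Exclusions become 20 + 2 = 22, and contraindicated but eligible falls from 1 to 0.

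**The case against.** The strongest reply is that the criterion was chosen deliberately. Section 4.2 describes ATHENA as leaving out recent NYHA IV heart failure and recent hospitalization for decompensation, with no referral limb. Exclusion 3 has that shape and is stricter, since it removes all of NYHA III, and item 4 adds the LVEF limit. This is possible, but it is not the reason Section 8.2 gives. That section derives the exclusion from a contraindication that includes referral, and it does not explain the omission.

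A second reply is that the prescriber is a safeguard. Section 6.2 has a physician generate the prescription, Section 2.2 points to the package insert, and Section 8.2 itself states the contraindication. Digoxin is handled in a similar way, as a prescribing contraindication and not an exclusion. This lowers the chance of harm. However, a refusal after randomization leaves an untreated participant in the intention-to-treat set, and the digoxin rule is at least repeated in the treatment sections.

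A third reply is that the profile is rare and mild. It needs four conditions at once. The question of interest in Section 9.3.2 describes patients without heart failure, and one recruitment count in Section 9.5 does the same. The mortality evidence is cited for the contraindicated group as a whole, not for a non-admitted NYHA II patient with LVEF above 40%. The points on rarity and mildness stand and limit the weight of the issue. The descriptions of a population without heart failure do not close the gap, because they are not eligibility criteria.

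Finally, the profile counts are unweighted and depend on the axes chosen. That is correct: they show that exactly one profile is uncovered, and they say nothing about patient numbers.

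**Conclusion.** The inconsistency is real and follows from the protocol's text alone. Exactly one clinical profile, NYHA II with LVEF above 40% and a decompensation in the last 4 weeks that led to referral without admission, is both contraindicated under Section 8.2 and eligible under Section 5.2. In other respects the exclusions are wider than the contraindication, but that does not protect this profile.

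The conclusion assumes that the contraindication is meant as Section 8.2 states it and that sites apply the listed criteria as written. The number of patients affected is not given and is probably small, and no risk estimate specific to them is available. Confidence is high on the mismatch and lower on how often it would matter in practice. The change should be made, on patient-safety grounds; the statistical design is unaffected.

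**What to change.** Extend the 4-week limb of exclusion 3 so that it covers either a hospitalization for heart failure or a decompensation of heart failure requiring referral to a specialist heart failure clinic. Leave the NYHA III–IV limb as it is. Make the same change in the Synopsis, in Section 5.2 and in the restatement in Section 8.2, and update the matching REDCap eligibility item.

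The cost is one phrase in three places and one database item. The change also excludes NYHA I patients referred without admission, whom Section 8.2 does not call contraindicated. That is consistent with the existing hospitalization limb, which applies whatever the class. If the sponsor prefers not to exclude them, the referral limb can be restricted to NYHA II, which still closes the gap and newly excludes one profile instead of two. Either way the effect on enrollment should be small, and sample size and power do not change.

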9.1. Statistical Hypotheses

The primary efficacy objective is to determine if treatment with dronedarone on top of usual care is superior to usual care for the prevention of unplanned cardiovascular hospitalization or death from any cause within 12 months of randomization in patients with first-detected atrial fibrillation.

- The null hypothesis is that the hazard rate of first unplanned cardiovascular hospitalization or death from any cause through 12 months of follow-up in the dronedarone + usual care arm is not different from the hazard rate in the usual care arm.

Key secondary efficacy objectives are to assess the efficacy of treatment with dronedarone on top of usual care versus usual care on

- WIN Ratio
- Time to first unplanned CV hospitalization
- All-cause mortality

There will also be a **patient reported outcomes** study. Patient reported change in quality of life at 12 months compared to baseline, assessed by the AFEQT and by the MAFSI AF-related quality of life questionnaires.

The key safety objective is to characterize the incidence of specific safety events of interest in patients taking dronedarone versus usual care (defined in **Table 3**).

9.1.1. Multiplicity Adjustment

Formal statistical hypothesis testing will be restricted to the primary objective and the WIN ratio (the first secondary objective). Type I error (one-sided $\alpha=0.025$) will be controlled for these objectives using the gatekeeping testing strategy adapted from Maurer & Bretz (2013),⁶³ accounting for one unblinded interim analysis. The details of multiplicity adjustment are described in Section 9.4 below.

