1. **WIN Ratio:** The WIN ratio will be the key secondary endpoint.³⁵ Among the randomized patients, every patient in the dronedarone arm will be compared with every patient in the usual care arm. Within each pair of patients, the component outcomes will be compared in descending order of importance until one of the patients in the pair demonstrates a better outcome compared with the other. For the purpose of this trial the hierarchy of component outcomes are shown in **Table 2**. The components in the WIN ratio hierarchy are similar to the endpoints considered in the recent EAST-AFNET4 trial.

Table 2. Hierarchy of Outcomes for the WIN Ratio

1. All-cause mortality
2. Ischemic stroke or systemic embolism
3. Hospitalization for new/worsening diagnosis of heart failure
4. Hospitalization for acute coronary syndrome

2. **Cardiovascular Hospitalizations:** Given the importance of CV hospitalization as an outcome³⁶ from a clinical perspective, patient perspective, and economic perspective³⁷, there will be two analyses of CV hospitalization. The key secondary endpoint will be time to first unplanned CV hospitalization (similar to the component of the primary endpoint). However, a second exploratory analysis of unplanned cardiovascular hospitalization using a method to account for repeated events (Anderson-Gill extension) will also be performed.
3. **All-cause mortality.** The final secondary endpoint of interest is all-cause mortality. For descriptive purposes, deaths will be categorized by the site investigators according to the following categories: cardiovascular and non-cardiovascular. Cardiovascular deaths will be further classified into arrhythmic vs non-arrhythmic according the modified Hinkle-Thaler criteria, as used in several landmark cardiovascular trials. Patients who are well and (1) have a witnessed sudden collapse or (2) those found dead, but known to be alive and well in the previous 24 hours (e.g. no signs or symptoms of cardiorespiratory distress) will be defined as having arrhythmic death.³⁸

Tertiary Outcomes:

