In addition to these routine safety reviews, an interim analysis for efficacy and futility of the primary objective is planned at approximately 50% of total information, i.e. when 50% of the expected total number of events (approximately 733 events, see **Table 4** below) are collected. The Lan-DeMets spending function similar to the O'Brien-Fleming boundaries will be used to monitor the efficacy of the primary outcome as a guide for the DSMB. See **Table 4** for the details of these procedures. This spending function is conservative in that priority is given to preserving power for the final analysis with the use of stringent stopping rules early in the study. For futility, conditional power will be calculated under originally hypothesized hazard ratio, the null hypothesis and the observed trend at the interim analysis and will be compared with 10%. The futility stopping rules will be considered non-binding by the DSMB in their review of interim data.

If the primary endpoint is declared to be statistically significant in the favorable direction at a one-sided alpha level of 0.025, WIN ratio as the first key secondary endpoint will be tested according to an OBF-like boundary. See **Table 4** for the details of these procedures.

Table 4. Significance level for the primary endpoint and WIN ratio

	At the interim analysis at 50%	At the final analysis	One-sided nominal significance level
One-sided significance level for the primary hypothesis	0.0153	0.0245	0.025
One-sided significance level for WIN ratio if the primary endpoint is declared significant	0.0153	0.0245	0.025

The Steering Committee will approve the timing of all interim analyses proposed by the DSMB. If the DSMB determines there is absence of futility, acceptable safety, and pre-trial assumptions regarding the endpoint event rate and other factors are correct, the trial will continue as planned.

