9.5. Sample Size Determination

- With a planned accrual time of 1.5 years, a fixed follow-up period of 1 year, an assumed lost to follow up of 20% before 12 months (assuming exponential distribution for time-to-censoring), a two-sample log-rank test with two-sided alpha of 0.05, a cumulative incidence function (CIF) of 30% at 12 months in the usual care arm, an assumed hazard ratio of 0.79, one interim analysis using the Lan-DeMets spending function similar to the O'Brien-Fleming boundaries, a planned sample size of 3000 patients (1500 patient per arm) provides approximately 89% study power as shown in the following table:

**Table 5. Study power and number of events with 3000 patients
Estimated by Markov chain Monte Carlo simulations with 10,000 iterations**

Hazard Ratio (Dronedarone vs. Usual care)	0.78	0.79	0.80
Nominal Power	0.92	0.89	0.86
Total number of events	730	733	737

[figure not shown]
- The study will be conducted at sites participating in the GWTG-AFIB Registry. Some sites will be centers that are established GWTG-AFIB sites and others will be recruited to participate in GWTG-AFIB for the purpose of this study. We will attempt to achieve a total of up to 200 sites. There have been more than 40,000 patients included in the GWTG-AFIB Registry. For the purpose of this pragmatic trial, patients will be approached at the time of their first-detected AF episode. Preliminary query of the GWTG-AFIB database suggests that greater than 1400 patients were enrolled each year in GWTG with new-onset AF and no heart failure. Using the Jan 2020 GWTG-AFIB data harvest, there were a total of 8,192 patients meeting the inclusion/exclusion criteria (see Table 6). As we plan to include sites beyond GWTG-AFIB sites, we plan to enrol 3000 patients in 18 months.

Table 6. Distribution of Admissions for GWTG-AFIB Registry Patients

Admission Year	Frequency (patients)	Percent	Cumulative Frequency (patients)	Cumulative Percent
2013	65	0.79%	65	0.79%
2014	390	4.76%	455	5.55%
2015	1229	15.00%	1684	20.56%
2016	1429	17.44%	3113	38.00%
2017	1750	21.36%	4863	59.36%
2018	1871	22.84%	6734	82.20%
2019	1458	17.80%	8192	100.00%

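### Two of the three key secondary objectives are left outside the testing sequence, although adding them at its end costs the earlier tests nothing, once Table 4's interim level is corrected

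*Protocol*

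**What the plan says.** Section 9.1 of the protocol introduces its list with "Key secondary efficacy objectives are to assess the efficacy of treatment with dronedarone on top of usual care versus usual care on" and then names the WIN ratio, time to first unplanned CV hospitalization and all-cause mortality.

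Section 9.1.1 narrows the scope: "Formal statistical hypothesis testing will be restricted to the primary objective and the WIN ratio (the first secondary objective"). Type I error, one-sided 0.025, "will be controlled for these objectives using the gatekeeping testing strategy adapted from" a published graphical method for group sequential trials, allowing for one unblinded interim analysis.

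Section 9.4 opens the gate when the primary endpoint is "statistically significant in the favorable direction at a one-sided alpha level of 0.025"; then "WIN ratio as the first key secondary endpoint will be tested according to an OBF-like boundary". Table 4 has two rows only. The first reads "One-sided significance level for the primary hypothesis 0.0153 0.0245 0.025" (interim, final, overall), and the WIN ratio row carries the same three numbers.

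The analysis sections follow suit. The primary endpoint (9.3.2) and the WIN ratio (9.3.3.1) get a P-value. CV hospitalization (9.3.3.2, main analysis) and mortality (9.3.3.3) get a hazard ratio with a nominal 95% interval and no P-value. One place departs from this: section 9.3.7 speaks of testing the primary and the key secondary objectives, without distinction, in the on-treatment population.

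**The concern.** In a fixed sequence, the full level passes on when a hypothesis is rejected. The plan builds such a sequence and stops it at step two, so the level released by a significant WIN ratio is not used. A trial that succeeds on both the primary endpoint and the WIN ratio could still make no error-controlled statement about CV hospitalization or death as endpoints in their own right, although both are listed as key secondary objectives.

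The loss falls mainly on CV hospitalization. It is a component of the primary endpoint. The WIN hierarchy (Table 2) counts hospitalization only for heart failure and acute coronary syndrome, so the one tested secondary does not stand in for it. Because the protocol states that testing is restricted, a later analysis plan that extended it would contradict the protocol.

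**Working it through.** **1. The plan's own figures.** Section 9.5 plans on "a two-sample log-rank test with two-sided alpha of 0.05", hazard ratio (HR) 0.79, 733 events and power 0.89. Schoenfeld's formula gives power = Φ(√D/2 × |ln HR| − z) = Φ(√733/2 × 0.2357 − 1.960) = Φ(3.191 − 1.960) = 0.891. The two-look group-sequential calculation gives 0.890. The stated power reproduces.

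**2. Table 4.** The Lan-DeMets O'Brien-Fleming-type function spends 2[1 − Φ(z₀.₀₁₂₅/√t)] by information fraction t. At t = 0.5 this is 2[1 − Φ(2.2414/0.7071)] = 2[1 − Φ(3.170)] = 0.00153. Solving for the final level with correlation √0.5 between looks gives 0.0245, as printed. The final level therefore belongs with 0.00153, not with the printed 0.0153.

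| Interim / final level | Overall one-sided error |
|---|---|
| 0.00153 / 0.0245 | 0.0250 |
| 0.0153 / 0.0245 (as printed) | 0.0337 |

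**3. Cost of extending the sequence.** Order the hypotheses: primary, WIN ratio, CV hospitalization, mortality. A false rejection requires the first true null in this order to cross its own boundary. If every boundary has overall level 0.025, family-wise error is at most 0.025 whatever follows. A simulation of 1,000,000 trials with corrected levels, two looks and assumed correlations between endpoints gave 0.0252 under the global null with two tests and 0.0252 with four. The mixed-null settings that were run gave at most 0.0123. The tests of the primary endpoint and WIN ratio are unchanged.

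**4. Marginal power for CV hospitalization.** Assume HR 0.79 and that 0-15% of the 733 first events are deaths. At one-sided 0.0245 (z = 1.969):

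- 733 events: Φ(3.191 − 1.969) = 0.89
- 733 × 0.85 = 623 events: Φ(2.942 − 1.969) = 0.83

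**5. The WIN ratio gate.** The protocol gives no component rates, so these are assumptions: 12-month usual-care death 2-5%, non-fatal WIN events 3-7%, HR 0.75-1.0 on each. As a stand-in for the win ratio, take a log-rank test on the first WIN component with 20% exponential loss (γ = −ln 0.8 = 0.223). Per arm, events = 1500 × λ/(λ+γ) × [1 − exp(−(λ+γ))], where λ sums −ln(1 − rate) over the two components, each multiplied by its HR in the dronedarone arm.

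- HR 1.0 on both: power equals the test level, 2.4%.
- Benefit on death only (HR 0.75): 6-22%.
- Top corner (death 5%, non-fatal 7%, HR 0.75 on both): λ = 0.124 and 0.093, about 276 events, Φ(√276/2 × 0.2877 − 1.969) = Φ(0.42) = 66%.

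The range is about 2-66%. CV hospitalization is reached only through this gate, so the chance of a controlled claim is 0% as written and at most of this order if appended.

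**6. Mortality.** Assume 12-month usual-care death 1-5% and HR 0.70-0.85, with deaths = 3000 × 0.9 × rate × (1 + HR)/2 (0.9 is a rough allowance for loss).

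- 1%, HR 0.85: 25 deaths, power 0.06
- 5%, HR 0.70: 115 deaths, power 0.48

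Both figures are marginal, before three earlier gates.

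**The case against.** The best defence is that nothing here is wrong. The restriction is stated openly and carried through the P-values, the nominal intervals and Table 4. Section 9.1 promises only to assess efficacy. CV hospitalization and death are the two components of the primary endpoint, and death is the top WIN tier, so reporting them with nominal intervals is respectable practice. All of this stands, and it is why the point is a suggestion for improvement.

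Two stronger readings are tempting. A reader might infer that the protocol contradicts itself, because section 3 calls the WIN ratio the key secondary endpoint and then says "The key secondary endpoint will be time to first unplanned CV hospitalization". In context that sentence separates the time-to-first analysis from the exploratory recurrent-event analysis; it does not promise a confirmatory test. A reader might also infer that the extension keeps error at 0.025 with Table 4 left as printed. It does not: at the printed levels the primary test alone runs at about 0.0337.

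It is also fair that the extension is a little more than two copied rows. Half of the primary events need not mean half of the deaths or half of the WIN events, so each added endpoint needs its own levels. What the defence does not show is any cost to the first two tests.

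**Conclusion.** The point holds as a free improvement of low severity. As written, no result can support an error-controlled claim on CV hospitalization or on mortality. Continuing the sequence makes both possible with no change to the levels or power of the first two tests, provided every boundary is valid, which Table 4's printed interim level is not.

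The benefit is conditional and mostly concerns CV hospitalization, which is well powered once reached but sits behind a WIN ratio of very uncertain power. The stand-in range rests on assumed event rates and is not a hierarchical win ratio calculation; its lower end is simply the false-positive rate when the components show no effect. For mortality the practical gain is small. The one wording conflict on testing scope is in section 9.3.7.

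**What to change.** 1. In Table 4, replace the interim level with the value from the named Lan-DeMets O'Brien-Fleming-type function, about 0.00153 one-sided at 50% information. This is needed whether or not the sequence is extended.
2. In 9.1.1, 9.4 and Table 4, continue the sequence as primary, WIN ratio, time to first unplanned CV hospitalization, all-cause mortality. Test each at overall one-sided 0.025, and only if all earlier hypotheses are rejected.
3. Pre-specify interim and final levels for each added endpoint, from the spending function at that endpoint's own information fraction, and fix the order before unblinding.
4. Align 9.3.7 with the final testing scope. If the sponsor keeps the restriction, reword 9.3.7 so that it does not describe the untested objectives as tested.

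The cost is two rows in Table 4, a short addition to 9.1.1 and 9.4, and the work of setting the added levels. It takes no patients, no alpha, and no power from the primary endpoint or the WIN ratio.
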